#### 10.3.3.3 Assessment of Procedure Pain

Procedure pain will be assessed by asking subjects to rate their index knee for pain (1) at rest prior to pre-medication; (2) prior to IA lidocaine (without epinephrine); (3) at rest 10 minutes (±2 minutes) after IA lidocaine (without epinephrine); (4) at 30 minutes (±5 minutes) after IA injection of CNTX-4975-05 and (5) at rest at the 1-hour and 2-hour time points after IA injection of CNTX-4975-05 (±10 minutes).

Categorical scoring will be used: none, mild, moderate, moderately severe, or severe.

#### 11 ADVERSE EVENTS

#### 11.1 Definitions

#### 11.1.1 Adverse Events

An AE is defined as any untoward medical occurrence in a patient or clinical investigation subject administered a pharmaceutical product that does not necessarily have a causal relationship with the product. An AE can therefore be any unfavorable and unintended sign (including a new, clinically important abnormal laboratory finding), symptom, or disease, temporally associated with the product, whether or not related to the product.

Pre-existing diseases or conditions will not be considered AEs unless there is an increase in the frequency or severity, or a change in the quality of the disease or condition (worsening of a pre-existing condition is considered an AE).

Events occurring in subjects treated with placebo or active comparator or during treatment-free periods of the study are also considered AEs.

### 11.1.2 Unexpected Adverse Event

An expected AE is one for which the nature or severity is consistent with the known AE profile of the product. For an investigational product, the known information is contained in the IB. For a marketed product, the known information is contained in the current package insert for the product.

An unexpected adverse event (UAE) is one for which the specificity or severity is not consistent with the current IB. For example, hepatic necrosis would be unexpected (greater severity) if the IB only listed elevated hepatic enzymes or hepatitis. Likewise, cerebral thromboembolism and cerebral vasculitis would be unexpected (greater specificity) if the IB only listed cerebral vascular accidents.

Furthermore, reports that add significant information on specificity or severity of a known, already documented adverse reaction constitute unexpected events. Examples would be (a) acute renal failure as an expected adverse reaction with a subsequent new occurrence of interstitial nephritis (interstitial nephritis would be unexpected) and (b) hepatitis with a first occurrence of fulminant hepatitis (fulminant hepatitis would be unexpected).

#### 11.1.3 Serious Adverse Events

An SAE is any untoward medical occurrence that at any dose

- results in death
- is life-threatening NOTE: The term "life-threatening" in the definition of "serious" refers to an event in which the patient was at risk of death at the time of the event; it does not refer to an event

which hypothetically might have caused death if it were more severe.

• requires inpatient hospitalization or prolongation of existing hospitalization NOTE: Inpatient hospitalization is defined as 24 hours in a hospital or an overnight stay. An elective hospital admission to treat a condition present before exposure to the test drug, or a hospital admission for a diagnostic evaluation of an AE, does not qualify the condition

or event as an SAE. Further, an overnight stay in the hospital that is only due to transportation, organization, or accommodation problems and without medical background does not need to be considered an SAE.

- results in persistent or significant disability/incapacity
- is a congenital anomaly

NOTE: A congenital anomaly in an infant born to a mother who was exposed to the IP during pregnancy is an SAE. However, a newly diagnosed pregnancy in a subject that has received an IP is not considered an SAE unless it is suspected that the IP(s) interacted with a contraceptive method and led to the pregnancy.

• is an important medical event

NOTE: Medical and scientific judgment should be exercised in deciding whether it is appropriate to consider other situations serious, such as important medical events that may not be immediately life-threatening or result in death or hospitalization but may jeopardize the patient or may require intervention to prevent one of the other outcomes listed in the definition above.

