## 5.1.2 Clinical Experience

The efficacy and safety of CNTX-4975 in subjects with moderate-to-severe OA knee pain has been investigated in 7 studies. In an initial dose-ranging study in 16 subjects

(SAEs) was low, and none was thought to be related to the IP. Three of the studies reported no SAEs. In 1 study, an SAE was reported as possibly related (CNTX-4975-2-004-1, indication Morton's neuroma) and involved T-wave inversion. However, this event occurred in the placebo group and resolved without further treatment. Three other SAEs were listed as unrelated and involved chest pain (CNTX-4975-2-002-1, indication OA), femoral hernia (CNTX-4975-2-006-2; indication OA), and menorrhagia (CNTX-4975-2-005-2; indication lateral epicondylitis). One SAE was worsening of previous shoulder OA in study CNTX-4975-OA-502, noted as unrelated, with the subject continuing in the trial.

Most of the systemic adverse events (AEs) occurred with similar frequency in capsaicin-treated (all doses combined) compared to placebo-treated subjects. The exception from this was the frequency of initial pain from the injection. Intra-articular injection of capsaicin into the knee produced short-term pain, most often for a period less than 30 minutes. In the preliminary analysis of Study 114-02P, subjects typically indicated that the pain was tolerable (mean peak pain 5.4 on the 0-10 Numeric Pain Rating Scale [NPRS]). However, 4 of 40 subjects, asked to indicate whether the pain was tolerable, indicated that the pain was intolerable. In all instances, the

procedure pain was short-lived (typically under 1 hour) and was under satisfactory control at the time the patient was discharged from the clinic.

Study 4975-OA-501 included 30 subjects with OA of the knee whose index knee was treated with CNTX-4975 IA. The focus of this study was to further manage procedural pain. The results suggested the best approach included a combination of opioid pre-medication, 15 mL of lidocaine (2%, without epinephrine) IA 15-30 minutes before IP injection, combined with joint cooling.

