#### 11.2.7.2 Non-serious Adverse Events

Non-serious AEs will be recorded in the eCRF and reported by Therapeutics Corp.

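### The note to the hospitalization criterion in 11.1.3 exempts diagnostic admissions without limit, so some unplanned overnight work-ups of a new AE could be classed as non-serious

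*Combined protocol and SAP*

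**What the plan says.** Section 11.1.3 lists, as one ground for seriousness, an event that "requires inpatient hospitalization or prolongation of existing hospitalization". The note beneath it sets the threshold: "Inpatient hospitalization is defined as 24 hours in a hospital or an overnight stay". It then takes three kinds of stay out of the criterion:

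- "An elective hospital admission to treat a condition present before exposure to the test drug";
- an admission made to investigate an AE: "or a hospital admission for a diagnostic evaluation of an AE, does not qualify the condition" or event as an SAE;
- an overnight stay that is "only due to transportation, organization, or accommodation problems and without medical background does not need to be considered an SAE".

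The other grounds (death, life-threatening, lasting or significant disability, congenital anomaly, important medical event) stand separately in the same section. Section 11.2.3.2 has the investigator judge seriousness against 11.1.3.

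That judgement decides what happens next. SAEs are reported within 24 hours (11.2.7.1) and summarized separately (13.4.4.1). For the rest, 11.2.7.2 says "Non-serious AEs will be recorded in the eCRF" and sets no such clock. Section 12 states that there is no data safety monitoring board, and 13.2 bases the sample size of about 850 on regulatory safety requirements.

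**The concern.** The second exemption turns on the purpose of the admission and on nothing else. A subject kept in hospital overnight after the injection for unexplained chest pain, syncope or shortness of breath meets the stated threshold. At onset, however, the admission can fairly be described as diagnostic. Whether it counts as serious then depends on how the site words the reason for admission.

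Three features of the plan give this some weight.

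- Without a monitoring board, and with interim safety reviews only optional (13.4.5), the 24-hour SAE report is an important prompt route to the sponsor.
- Bilaterally treated subjects (target of at least 150) are scheduled for a second injection around Day 7, with a window of -2 to +5 days. Section 11.2.5 has the sponsor decide whether a subject with an AE continues. An admission after the first injection that is classed as non-serious has no 24-hour route to the sponsor before that visit.
- Regimens are assigned by site (9.5), and AE summaries are shown by injection procedure (13.4.4.1). A site's labelling habit therefore falls within a single regimen.

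**Working it through.** No SAE rate, admission rate or power figure is stated for this point, so there is no plan figure to reproduce. The check is mainly of the text.

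**Step 1: compare the limits on the three exemptions.**

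| Exemption in the 11.1.3 note | Elective only | Condition present before exposure only | Non-medical stay only |
|---|---|---|---|
| Admission to treat an existing condition | yes | yes | no |
| Admission to evaluate an AE | no | no | no |
| Logistics stay | no | no | yes |

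The word elective does not carry over to the second limb, which has its own article and noun. Nor can that limb be confined to stable pre-existing disease, because 11.1.1 excludes pre-existing conditions from AEs unless they worsen or change. The clause therefore reaches new or worsened events by its own terms.

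**Step 2: apply the definition to three hypothetical subjects, each admitted overnight and unplanned after an injection.**

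1. Admitted to treat an AE: the hospitalization criterion is met, no exemption applies, and the event is an SAE.
2. Admitted for work-up and at risk of death: the life-threatening ground, which "refers to an event in which the patient was at risk of death at the time of the event", applies separately, and the event is an SAE.
3. Admitted for work-up, with no death, danger to life or lasting disability: the threshold is met but the exemption removes it. Only the important-medical-event ground remains. That ground rests on judgement and is described for events that may not lead to hospitalization, so it fits a hospitalized subject awkwardly.

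The gap is case 3. Section 11.2.4 adds to the uncertainty: it names hospitalization as an example under seriousness and mentions no exemption.

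**Step 3: scale.** The input is N = 850 (13.2). The number of reclassified subjects, k, is assumed.

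- Change in the SAE rate for each subject whose only SAE is reclassified: 1/850 = 0.12 percentage points.
- Two-sided 95% Clopper-Pearson upper limit: the 0.975 quantile of Beta(k + 1, 850 - k). For k = 0 this is 1 - 0.025^(1/850) = 0.43%.

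| Subjects with an SAE (assumed) | Rate | 95% upper limit |
|---|---|---|
| 0 | 0% | 0.43% |
| 1 | 0.12% | 0.65% |
| 3 | 0.35% | 1.03% |
| 5 | 0.59% | 1.37% |

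For example, if three subjects each had one SAE and all three were reclassified, the reported upper limit would fall from 1.03% to 0.43%. If the five regimens were of equal size (an assumption: 850/5 = 170), one reclassified subject would move that regimen's rate by 1/170 = 0.59 percentage points.

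**The case against.** The clause is an express exception written into the note of the criterion it qualifies. A reader might infer that the protocol contradicts itself, but a rule with a stated exception is not two incompatible rules. This part of the objection stands: the fault is an exception drawn too widely.

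A reader might also infer that unplanned post-injection admissions in general drop out of SAE reporting. The text does not support that, as cases 1 and 2 show. Nor are exempted events lost: 11.2.4 requires every AE to be documented, and 13.4.4.1 tabulates AEs by severity and relationship. Suspected anaphylaxis, for which syncope and dyspnea are listed features, has its own monitoring, sampling and timed recording under 11.2.1. All of this stands and narrows the point to classification and speed of reporting.

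The programme history offers no direct evidence either. Section 5.1.2 says "Three other SAEs were listed as unrelated and involved chest pain", which may look like an example of the problem. That event was captured as an SAE, and the text does not say whether an admission took place or why.

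Finally, the Safety Management Plan cited in 11.2.7.1 is a separate document, and the opening of 11.2.1 was not available. An additional reporting rule in either cannot be ruled out.

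What the objection does not answer is case 3. The remaining safeguard there is discretionary, and the phrase saying that such an admission does not make the condition or event an SAE could be misread as overriding the other grounds too.

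**Conclusion.** The concern holds in limited form. As written, 11.1.3 allows some unplanned overnight admissions for work-up of a new post-injection AE to be classed as non-serious. This happens when the admission is labelled diagnostic and no other ground is invoked. What is lost is the 24-hour report and a place in the SAE summary; the AE record remains.

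The number affected is unknown. It would be tempting to state what share of SAEs goes missing, but that needs an admission rate, the share labelled diagnostic and the share rescued by another criterion. The documents give none of these. The supportable figure is about 0.12 percentage points per reclassified subject at N = 850, assuming that subject has no other SAE. Safety analyses are planned without formal inference unless otherwise noted (13.4.4), so no stated trial conclusion is shown to change. The correction is still worth making because it is cheap, the subjects concerned are in hospital, and the trial was sized for safety.

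**What to change.** Reconcile the note in 11.1.3 with its criterion in one of two ways: delete the diagnostic-evaluation clause, or limit it to elective or pre-planned admissions for a condition present before exposure. Either way, an unplanned stay of 24 hours or overnight for a new or worsened AE should count as hospitalization. The exemptions for elective treatment and for logistics stays can remain.

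For admissions already recorded, query the investigators, who assign seriousness under 11.2.3.2, and ask them to reassess under the corrected definition before the SAE tables in 13.4.4.1 are produced. The sponsor should not reclassify on its own.

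The cost is an edit to one clause through a protocol amendment (14.8), a memo to sites, some queries, a few more expedited reports and a slightly higher reported SAE rate.

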### 11.1.4 Significant Adverse Events

Other significant AEs are defined as marked hematological and other laboratory abnormalities (other than those meeting the definition of serious) and any events that led to an intervention, including withdrawal of IP, dose reduction, or significant additional concomitant therapy.

### 11.1.5 Treatment-Emergent Adverse Events

An AE is defined as treatment emergent if the first onset or worsening is after the first administration of IP.

#### 11.2 Management of Adverse Events

Adverse events will be collected from the time of signing the ICF through the Week 8/ET Visit.

### **Anaphylactic Reaction**

An anaphylactic reaction is a rapid onset serious allergic reaction that has a variety of symptoms and outcomes, which can include death. An anaphylactic reaction typically has symptoms and signs starting over minutes to hours. Anaphylaxis causes more than one of the following: low

blood pressure, lightheadedness, shortness of breath, an itchy rash, throat or tongue swelling, and vomiting.

## **Anaphylactoid reaction**

These reactions produce the same clinical signs and symptoms anaphylactic reactions, but are not IgE mediated, but instead occur through a direct non-immune-mediated release of mediators from basophils and/or mast cells or can manifest from direct complement activation.

All subjects must be monitored for at least 30 minutes (or longer, as required by the protocol) after study drug injection to ensure that they do not have a hypersensitivity reaction/anaphylaxis. Vital signs (VS) are to be done pre-injection and 5 minutes after the injection, standing and sitting, and then vital signs must now be taken at 15 and 30 minutes (sitting only) after injection of study drug

Any subject that meets the criteria for anaphylaxis or anaphylactoid reactions, as described in the paper by Sampson et al. (2006) (see Appendix C) following the first/prior injection is prohibited from being re-treated with study drug.

### Clinical Criteria for Diagnosing Anaphylaxis

Anaphylaxis is highly likely when any **one of the following 3 criteria** are fulfilled:

- 1. Acute onset of an illness (minutes to several hours) with involvement of the skin, mucosal tissue, or both (eg, generalized hives, pruritus or flushing, swollen lips-tongue-uvula), AND AT LEAST ONE OF THE FOLLOWING:
  - a. Respiratory compromise (eg, dyspnea, wheeze-bronchospasm, stridor, reduced PEF, hypoxemia)
  - b. Reduced BP or associated symptoms of end-organ dysfunction (eg, hypotonia [collapse], syncope, incontinence)
- 2. Two or more of the following that occur rapidly after exposure to a likely allergen for that patient (minutes to several hours):
  - a. Involvement of the skin-mucosal tissue (eg, generalized hives, itch-flush, swollen lips-tongueuvula)
  - b. Respiratory compromise (eg., dyspnea, wheeze-bronchospasm, stridor, reduced PEF, hypoxemia)
  - c. Reduced BP or associated symptoms (eg, hypotonia [collapse], syncope, incontinence)
  - d. Persistent gastrointestinal symptoms (eg, crampy abdominal pain, vomiting)
- 3. Reduced BP after exposure to known allergen for that patient (minutes to several hours):
  - a. Infants and children: low systolic BP (age specific) or greater than 30% decrease in systolic BP\*
  - b. Adults: systolic BP of less than 90 mm Hg or greater than 30% decrease from that person's baseline

Source: Sampson et al. (2006)

Abbreviations: PEF, Peak expiratory flow; BP, blood pressure.

\* Low systolic blood pressure for children is defined as less than 70 mmHg from 1 month to 1 year, less than (70 mmHg +  $[2 \times age]$ ) from 1 to 10 years, and less than 90 mmHg from 11 to 17 years.

Page 63 of 89

Amendment 2 Version: 3.0

13-Jun-2019

In the event of an anaphylactic reaction or anaphylactoid event, institute treatment immediately, as outlined in Appendix C. Note also that a serum tryptase blood level must be obtained using the Vacutainer tube provided.

All anaphylactic and anaphylactoid events (e.g. rash, dyspnea, gastrointestinal symptoms) must be recorded with the time that the events occurred and resolved, and treatments (e.g. epinephrine) should be recorded with their time of administration.

#### 11.2.2 Collection

The investigator is responsible for the detection and documentation of events meeting the criteria and definition of an AE or SAE described previously. At each visit, the subject will be allowed time to spontaneously report any issues since the last visit or evaluation. The investigator will then monitor and/or ask about or evaluate AEs using nonleading questions, such as

- "How are you feeling?"
- "Have you experienced any issues since your last visit?"
- "Have you taken any new medications since your last visit?"

Any clinically relevant observations made during the visit will also be considered AEs.

#### 11.2.3 Evaluation

#### 11.2.3.1 Severity of Adverse Events

The clinical severity of an AE will be classified as

Mild Usually transient and may require only minimal treatment or therapeutic

intervention. The event does not generally interfere with usual activities of

daily living.

Moderate Usually alleviated with additional specific therapeutic intervention. The event

interferes with usual activities of daily living, causing discomfort but poses no

significant or permanent risk of harm to the subject.

Severe Interrupts usual activities of daily living, or significantly affects clinical status,

or may require intensive therapeutic intervention.

It is important to distinguish between severe AEs and SAEs. Severity is a classification of intensity, whereas an SAE is an AE that meets serious criteria, as described in Section 11.1.3.

#### 11.2.3.2 Seriousness

The investigator is to evaluate whether the AE meets serious criteria, as described in Section 11.1.3.

#### 11.2.3.3 Action(s) Taken

Action(s) taken may consist of

Dose An indication that a medication schedule was modified by addition; either by

changing the frequency, strength or amount. increased

Amendment 2 Version: 3.0 13-Jun-2019

Dose not changed	An indication that a medication schedule was maintained.
Dose reduced	An indication that a medication schedule was modified by subtraction, either by changing the frequency, strength or amount.
Drug interrupted	An indication that a medication schedule was modified by temporarily terminating a prescribed regimen of medication.
Drug withdrawn	An indication that a medication schedule was modified through termination of a prescribed regimen of medication.
Not applicable	Determination of a value is not relevant in the current context.
Unknown	Not known, not observed, not recorded, or refused.

#### 11.2.3.4 Outcome at the Time of Last Observation

- The outcome at the time of last observation will be classified as
- Recovered/resolved
- Recovered/resolved with sequelae
- Recovering/resolving
- Not recovered/not resolved
- Fatal\*
- Unknown

### 11.2.3.5 Adverse Event Relationship to Investigational Product

The investigator must make an assessment of each AE's relationship to the IP. The categories for classifying the investigator's opinion of the relationship are listed below.

Not related	An AE with sufficient evidence to accept that there is no causal relationship to IP administration (e.g., no temporal relationship to drug administration, because the drug was administered after onset of event; investigation shows that the drug was not administered; another cause was proven).
Unlikely related	An AE, including laboratory test abnormality, with a temporal relationship to IP administration that makes a causal relationship improbable, and in which other drugs, events or underlying disease provide plausible explanations.
Possibly related	An AE with a reasonable time sequence to administration of the IP, but which could also be explained by concurrent disease or other drugs or events. Information on drug withdrawal may be lacking or unclear.

\*Only select fatal as an outcome when the AE results in death. If more than one AE is possibly related to the subject's death, the outcome of death should be indicated for each such AE. Although "fatal" is usually an event outcome, events such as sudden death or unexplained death should be reported as SAEs.

Related

An AE occurring in a plausible time relationship to IP administration and which cannot be explained by a concurrent disease or other drugs or events. The response to withdrawal of the drug (dechallenge) is clinically reasonable.

#### 11.2.4 Documentation

All AEs occurring within the period of observation for the study must be documented in the eCRF with the following information, where appropriate. (The period of observation for the study is described in Section 11.2.)

- AE name or term
- When the AE first occurred (start date and time)
- When the AE stopped (stop date and time or an indication of "ongoing")
- Severity of the AE
- Seriousness (hospitalization, death, etc.)
- Actions taken
- Outcome
- Investigator opinion regarding the AE relationship to the IP(s)

